6.7.8. Management of Fatigue

Other causes of fatigue should be evaluated (eg, infection, disease progression and hematological, electrolyte, and endocrine abnormalities). Dose-modification and/or low-dose corticosteroids may be considered. General guidelines from [Table 7](#) can be used to manage fatigue as it may be an overlapping toxicity for both RMC-4630 and sotorasib.

6.7.9. Pneumonitis

Respiratory symptoms such as dyspnea, cough, shortness of breath, etc, should be investigated with a chest X-ray or chest computed tomography (CT) scan. Evaluate for possible infections and other causes of respiratory compromise including progressive pulmonary disease, cardiac dysfunction, or any environmental factors, etc.

If the diagnosis of ILD or pneumonitis is confirmed, permanently discontinue sotorasib and RMC-4630. Initiate treatment per investigator judgement with corticosteroids and supportive care as per institutional guidelines.

6.7.10. Management of Fluid Retention/Overload Events

Evaluate for other or concomitant causes including medications. Treat according to institutional guidelines including the cessation of other medications known to be associated with the development of fluid retention/overload events, if clinically indicated. General guidelines from [Table 7](#) can be used to manage fluid retention/overload events as it is considered to be an overlapping toxicity for both RMC-4630 and sotorasib.

7.2. Subject Discontinuation/Withdrawal from the Study

Subjects may withdraw from the study at any time at their own request, or they may be withdrawn at any time at the discretion of the investigator for safety, behavioral, compliance, or administrative reasons. These withdrawals are expected to be uncommon.

A subject may be withdrawn from the study for any of the following reasons:

- Subject's withdrawal of consent for participation in the study
- Sponsor's decision to terminate the study
- Subject is lost to follow-up
- Death

Upon permanent discontinuation of study treatment for any reason, including for subjects in the Extended-Use Phase, an end-of-treatment (EOT) visit should be completed within 30 days after the last dose of study treatment or before any new antitumor treatment is started.

Following the EOT visit, subjects will be considered to have completed the study. Survival follow up will be discontinued for subjects currently in LTFU.

If the subject withdraws consent for disclosure of future information, the Sponsor may retain and continue to use any data collected before such a withdrawal of consent.

If a subject withdraws from the study, he/she may request in writing destruction of any samples taken and not tested, and the investigator must document this in the site study records.

7.3. Lost to Follow-Up

A subject will be considered lost to follow-up if he/she repeatedly fails to return for scheduled visits and is unable to be contacted by the study site.

The following actions must be taken if a subject fails to return to the clinic for a required study visit:

- The site must attempt to contact the subject and reschedule the missed visit as soon as possible, counsel the subject on the importance of maintaining the assigned visit schedule and determine whether or not the subject wishes to and/or should continue in the study.
- Before a subject is deemed lost to follow-up, the investigator or designee must make every effort to regain contact with the subject (where possible, 3 telephone calls and, if necessary, a certified letter to the subject's last known mailing address, or local equivalent methods). These contact attempts should be documented in the subject's medical record.
- Should the subject continue to be unreachable, he/she will be considered to have withdrawn from the study.

Study discontinuation at specific sites or of the study as a whole are described in [Appendix 1 \(Study and Site Closures\)](#).

8. STUDY ASSESSMENTS AND PROCEDURES

- Study procedures and their timing are summarized in the SoA ([Table 1](#)). Protocol waivers or exemptions are not allowed.
- Immediate safety concerns should be discussed with the Sponsor immediately upon occurrence or awareness to determine if the subject should continue or discontinue study treatment.
- Adherence to the study design requirements, including those specified in the SoA, is essential and required for study conduct.
- All screening evaluations must be completed and reviewed to confirm that potential subjects meet all eligibility criteria. The investigator will maintain a screening log to record details of all subjects screened and to confirm eligibility or record reasons for screening failure, as applicable.
- Procedures conducted as part of the subject's routine clinical management (eg, blood count) and obtained before signing of the ICF may be used for screening purposes provided the procedures met the protocol-specified criteria and were performed within the time frame defined in the SoA.
- The maximum amount of blood collected from each subject over approximately 9 months (13- to 14-cycle study duration), including any extra assessments that may be required, will not exceed 0.9 L. Repeat or unscheduled samples may be taken for safety reasons or for technical issues with the samples.

8.1. Efficacy Assessments

Subjects will be assessed for response using RECIST v1.1 (see [Appendix 6](#)), as assessed by the investigator. All measurable disease must be documented at screening and reassessed at each subsequent tumor evaluation. Measurable disease is required for each subject (Inclusion Criterion 3 [[Section 5.1](#)]). Response assessments will be assessed by the investigator based on physical examination (including measurement of cutaneous lesions) and CT scans or MRI. Imaging should include chest and abdomen (depending on primary tumor type, site of metastasis and investigator assessment). At the investigator's discretion, the imaging studies may be repeated at any time if disease progression is suspected. Additional studies, such as positron emission tomography (PET) or bone scans, should be performed if clinically indicated. Care should be taken to repeat the same modality used at screening throughout the study and to ensure all anatomy imaged at screening is again imaged at follow-up scans for any given subject. As part of the tumor assessment, physical examinations should include all areas of tumor involvement that are amenable to examination, including biopsy sites, lymph nodes, and bone tenderness, if applicable.

All imaging studies should be evaluated by a local radiologist with expertise in the imaging modality. The investigator is responsible for determining the overall response at each timepoint.

Radiological imaging and tumor assessments are required at screening and every 2 cycles starting from Cycle 3 (ie, every 6 weeks [± 1 week]) up to Cycle 9, every 4 cycles (ie, every 12 weeks [± 1 week]) thereafter and EOT. Radiographic response (CR and PR) requires

confirmation by a repeat scan at least 4 weeks after the first documentation of response and may be delayed until the next scheduled scan to avoid unnecessary procedures.

In the Extended-Use phase of the study, tumor imaging is not required per protocol. If required, imaging should be performed according to local standards of care and may be entered in the eCRF at the end of the extended use phase, if available.

8.2. Safety Assessments

Subjects will undergo the following safety assessments listed below and described in the following sections. Planned time points for all safety assessments are provided in the SoA ([Table 1](#)). Refer to the column on safety assessments for the Extended-Use phase of the study ([Table 1](#)) AEs, SAEs ([Section 8.3](#))

- Hematology, clinical chemistry, liver transaminases and bilirubin tests ([Section 8.2.6](#)), coagulation tests (PT, INR, and aPTT or PTT) and urinalysis.
- Vital signs ([Section 8.2.2](#))
- Body weight and height ([Section 8.2.3](#))
- Physical examination ([Section 8.2.1](#))
- 12-lead ECGs ([Section 8.2.4](#))
- ECHO/MUGA scans ([Section 8.2.5](#))
- Ophthalmologic examinations ([Section 8.2.8](#))
- Concomitant medications/procedures
- ECOG performance status ([Section 8.2.7](#))

The ISMC will review emergent safety data from the RMC-4630 program at regular intervals for all subjects during the trial in conjunction with data from other active RMC-4630 studies, described in [Section 8.3.6](#).

8.2.1. Physical Examinations

- A complete physical examination will include, at a minimum, assessments of the head, eyes, ears, nose, and throat (HEENT), dermatologic, cardiovascular, respiratory, GI (including assessments of liver and spleen), musculoskeletal, neurological, and lymphatic systems. Height and weight will also be measured and recorded. A symptom/AE directed physical examination should be performed as indicated by subject presentation or subject-reported symptoms or AEs.
- A limited examination should include an evaluation of the HEENT, dermatologic, cardiovascular, respiratory, and GI systems. A symptom/AE directed physical examination should be performed as indicated by subject presentation or subject-reported symptoms or AEs.
- Investigators should pay special attention to clinical signs related to previous serious illnesses.

8.2.2. Vital Signs

Vital signs will be measured, preferably in a seated position, after an approximately 5-minute rest. Vital signs will include temperature, systolic and diastolic blood pressure, pulse rate, pulse oximetry, and respiratory rate. Results should be recorded on the appropriate eCRF. In the Extended-Use phase, vital signs results will be recorded in subject's medical record.

8.2.3. Weight and Height

Weight should be measured throughout the study as indicated in the SoA ([Table 1](#)). Coats and shoes should be removed prior to measurement. Height should be measured at screening, without shoes.

8.2.4. Electrocardiograms

The 12-lead ECGs will be obtained as outlined in the SoA ([Table 1](#)) for all subjects using an ECG machine that automatically calculates the heart rate and measures pulse rate, QRS, QT, and QTcF intervals. Refer to [Section 7.1](#) for QTcF withdrawal criteria. Additional QTcF readings or continuous monitoring should be obtained to demonstrate improvement or resolution as per institutional guidelines. Subjects should be in the supine position after several minutes of inactivity before any study-related ECGs are conducted.

The ECGs can be evaluated by the Investigator and/or by a local cardiologist for a final assessment, and these results should be recorded in the eCRF. An evaluation by a cardiologist will not be required for routine follow-up of ECGs and will be at the discretion of the Principal Investigator/Sub-Investigator. However, evaluation by a cardiologist will be required if the subject experiences a cardiac AE/SAE or if the subject experiences a QTc/QTcF prolongation.

A single 12-lead ECG should be performed at Screening. The average of triplicate readings for assessing QTc interval may be used at Screening to determine eligibility. Triplicate 12-lead ECGs should be obtained on C1D1 and C1D15 predose and approximately 2 to 4 hours post-dose. Then a single pre-dose ECG should be obtained on D1 of every 2 cycles starting at C3 (eg, C3D1, C5D1, etc) and at EOT (see SoA [[Table 1](#)] for full schedule).

8.2.5. Echocardiograms/Multigated Acquisition Scans

All subjects must have their LVEF assessed by two-dimensional ECHO scan or MUGA scan as part of the screening procedure and as outlined in the SoA ([Table 1](#)). If a subject does not complete 2 cycles of study treatment, the EOT assessment for LVEF is not required, unless clinical signs or symptoms warrant additional imaging.

ECHO is the preferred method since it can detect wall motion abnormalities. However, in situations where an ECHO machine is not readily available or is technically limited, a MUGA scan may be obtained to evaluate LVEF. The same methodology should be used throughout the study and, to the greatest extent possible, at the same institution/facility.

The LVEF is to be calculated based on institutional guidelines and must be within institutional normal limits or 50%, whichever is lower, before a subject can enroll into the study. The LLN for the LVEF at the institution/facility should be recorded on the respective eCRF along with the LVEF result.

8.2.6. Clinical Safety Laboratory Assessments

- Refer to [Appendix 2](#) for the list of clinical laboratory tests to be performed and the SoA ([Table 1](#)) for the timing and frequency.
- The investigator is responsible for reviewing laboratory test results and determining whether an abnormal value in an individual study subject represents a clinically significant change from the subject's baseline values. In general, abnormal laboratory findings without clinical significance (based on the investigator's judgment) are not to be recorded as adverse events. However, laboratory value changes that require treatment or adjustment to current study therapy are considered adverse events. Where applicable, clinical sequelae (not the laboratory abnormality) are to be recorded as the adverse event. Refer to [Appendix 2](#) for additional information pertaining to reporting of potential Hy's Law cases.
- All laboratory tests with values considered clinically significantly abnormal during participation in the study after the first dose of study treatment until EOT should be repeated until the values return to normal or baseline or are no longer considered clinically significant by the investigator or Medical Monitor.
 - If such values do not return to normal/baseline within a period of time judged reasonable by the investigator, the etiology should be identified where possible, and the Sponsor notified.
 - All protocol required- laboratory assessments, as defined in [Appendix 2](#), must be conducted in accordance with the SoA ([Table 1](#)).
 - If laboratory values from non-protocol specified laboratory assessments performed at the institution's local laboratory require a change in subject management or are considered clinically significant by the investigator (eg, SAE, AE, or dose modification), then the results must be recorded in the eCRF.

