8.4. Dose Limiting Toxicity Criteria

Potential DLTs are defined as all AEs specified below that occur during the first cycle of study treatment and that are considered by the investigator to be related to RMC-4630 and/or sotorasib.

DLT criteria are outlined below as follows:

- An AE that results in permanent discontinuation of RMC-4630 or sotorasib
- An AE that results in a delay of > 2 weeks in the start of Cycle 2
- Febrile neutropenia
- Grade 4 neutropenia of any duration
- Grade 3 neutropenia lasting >7 days
- Grade 3 thrombocytopenia with Grade ≥ 2 bleeding
- Grade 4 thrombocytopenia
- Grade 4 anemia
- Grade ≥ 4 vomiting and diarrhea

- Grade 3 vomiting or diarrhea lasting >3 days despite optimal medical support
- Grade ≥ 3 nausea lasting 3 days or more, despite optimal medical support
- Grade ≥ 3 rash lasting 3 days or more despite optimal medical support
- Grade 3 AST or ALT elevation lasting >5 days or Grade ≥ 4 AST or ALT elevation of any duration
- Grade ≥ 3 bilirubin elevation
- Grade ≥ 3 QTc prolongation
- Retinal vein occlusion
- Any other Grade ≥ 3 AE with the following exceptions:
 - Grade 3 Fatigue lasting 7 days or less
 - Asymptomatic Grade 3 electrolyte abnormalities that last <72 hours, are not clinically complicated, and resolve spontaneously or respond to medical interventions
 - Grade 3 amylase or lipase that is not associated with symptoms or clinical manifestations of pancreatitis
 - Other select laboratory abnormalities that do not appear to be clinically relevant or harmful to the subject and/or can be corrected with replacement or modifications (eg, Grade 3 lymphopenia, Grade 3 hypoalbuminemia)
- Any subject meeting the criteria for a Hy's Law case (ie, severe DILI) will be considered a DLT. A Hy's Law case is defined as the following: AST or ALT values of $\geq 3 \times$ ULN, AND total bilirubin $>2 \times$ ULN or INR >1.5 in the absence of cholestasis and other causes (eg, viral hepatitis, other preexisting or acute liver disease, or another drug capable of the observed injury), to explain the observed liver related laboratory abnormalities.

If a subject experiences a DLT during the DLT evaluation period during Cycle 1 of the safety run-in period, sotorasib and/or RMC-4630 treatment should be modified according to [Table 6](#) and [Table 7](#).

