9.4.2. Safety Analyses

All DLT assessments will be performed on the DLT-evaluable population (see [Section 8.4](#) for DLT assessment details). All other safety analyses will be performed on the Treated Population. Safety analyses will be descriptive in nature, and will include analyses of DLTs, AEs, SAEs, AEs leading to study treatment discontinuation and/or dose modification, clinical laboratory tests, vital signs, and ECGs. AEs will be coded using Medical Dictionary for Regulatory Activities (MedDRA) coding dictionary. Unless otherwise specified, AEs will be summarized by primary MedDRA system organ classes and Preferred Term. Safety analyses will be summarized by the initial combination dose level. Safety analyses will be presented for each cohort separately and for the overall study population.

During dose expansion after the final expansion dose has been selected, evaluation of all Grade 4 or higher treatment-related adverse event rates will be conducted to assess if the unacceptable toxicity threshold has been reached. If this threshold is met, enrollment to dose expansion will be halted pending review of safety data. After reviewing the totality of data from both CodeBreaK 101C and cumulative data from this study, one of the following actions may be taken:

1. Terminate the study
2. Amend the protocol to potentially improve the benefit/risk for subjects (eg, increase safety monitoring, modify dose/schedule, mandate premedication)
3. Continue dose expansion without any changes

The stopping rules use a Bayesian approach to pause the enrollment if the posterior probability is $\geq 80\%$ that the Grade 4 or higher treatment-related adverse event rate is greater than 20%. The stopping boundaries shown in [Table 9](#) assume a prior distribution of Beta (0.4, 1.6). The operating characteristics with the pre-specified batch size of 10 new subjects are summarized in [Table 10](#).

Table 9: Stopping Boundary by Number of Subjects

Number of Subjects Treated	Number of Subjects with Grade 4 or Higher Treatment-Related Adverse Events to Halt Enrollment
10	≥ 4
20	≥ 6
30	≥ 9
40	Expansion complete

Table 10: Operating Characteristics of Stopping Rules

True Grade 4 or Higher Treatment-Related Adverse Event Rate	Probability of Early Stopping of Dose Expansion	Average Dose Expansion Sample Size
0.1	2.1%	39
0.15	9.7%	38
0.2	25.8%	34
0.25	47.7%	29
0.3	69.2%	23

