
• Any abnormal laboratory test results (hematology, clinical chemistry, or urinalysis) or other safety assessments (eg, electrocardiogram [ECG], radiological scans, vital signs measurements), including those that worsen from baseline, considered clinically significant in the medical and scientific judgment of the investigator (ie, not related to progression of underlying disease or laboratory value changes that require treatment or adjustment to current study therapy).• Exacerbation of a chronic or intermittent preexisting condition including either an increase in frequency and/or intensity of the condition.• New conditions detected or diagnosed after study treatment administration even though it may have been present before the start of the study.• Signs, symptoms, or the clinical sequelae of a suspected drug-drug interaction.• Signs, symptoms, or the clinical sequelae of a suspected overdose of either study treatment or a concomitant medication. Overdose per se will not be reported as an AE/serious adverse event (SAE) unless it is an intentional overdose taken with possible suicidal/self-harming intent. Such overdoses should be reported regardless of sequelae.

Events NOT Meeting the AE Definition

• The disease/disorder being studied or expected progression, signs, or symptoms of the disease/disorder being studied, unless more severe than expected for the subject's condition.• Medical or surgical procedure (eg, endoscopy, appendectomy): the condition that leads to the procedure is the AE.• Situations in which an untoward medical occurrence did not occur (social and/or convenience admission to a hospital).• Anticipated day-to-day fluctuations of preexisting disease(s) or condition(s) present or detected at the start of the study that do not worsen.

Definition of SAE

If an event is not an AE per definition above, then it cannot be an SAE, even if serious conditions are met (eg, hospitalization for signs/symptoms of the disease under study, death due to progression of disease).

A SAE is defined as any untoward medical occurrence that, at any dose:
a. Results in death
b. Is life threatening The term 'life threatening' in the definition of 'serious' refers to an event in which the subject was at risk of death at the time of the event. It does not refer to an event that hypothetically might have caused death if it had been more severe.

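### Section 8.2.6 has sites record the clinical sequela in place of the laboratory abnormality, which conflicts with the AE-grade counts behind the DLT criteria and the Grade 4 or higher stopping rule

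*Protocol*

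**What the plan says.** **Recording.** Section 8.2.6 first states that "laboratory value changes that require treatment or adjustment to current study therapy are considered adverse events". The next sentence is: "Where applicable, clinical sequelae (not the laboratory abnormality) are to be recorded as the adverse event".

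**DLTs.** Section 8.4 opens: "Potential DLTs are defined as all AEs specified below that occur during the first cycle of study treatment", limited to events the investigator considers related. The list includes "Grade 4 neutropenia of any duration", Grade 4 thrombocytopenia, Grade 4 anemia, and graded AST/ALT and bilirubin elevations. One item begins "Grade 3 thrombocytopenia with Grade" and goes on to require bleeding of Grade 2 or higher. A catch-all covers any other Grade 3 or higher "AE with the following exceptions".

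**Expansion rule.** Section 9.4.2 says that "evaluation of all Grade 4 or higher treatment-related adverse event rates will be conducted". It pauses enrollment at 4 or more of 10, 6 or more of 20, or 9 or more of 30 subjects. SAP 7.7 repeats the rule.

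**AE definition.** Appendix 3 allows an abnormal laboratory finding to be an AE. Its bullet on laboratory results ends in a parenthesis reading "not related to progression of underlying disease or laboratory value changes that require treatment or adjustment to current study therapy".

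**The concern.** Both safety rules work on recorded AE grades. Section 8.2.6, read as written, substitutes the sequela for the abnormality and does not ask for both. The sequela then carries its own CTCAE grade, which can be lower. For example, a related Grade 4 thrombocytopenia with Grade 2 epistaxis would enter the AE data as one Grade 2 event.

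The substitution can only lower the recorded Grade 4 or higher count, and it does so when the laboratory toxicity had a clinical consequence. What is at stake is the sensitivity of the enrollment pause, to a lesser extent the DLT count that guides escalation, and the severity tables listed in SAP 7.7.3. Section 2.1.1 lists anemia and thrombocytopenia among the potential risks of RMC-4630, so the case is not remote.

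**Working it through.** **1. Is there a laboratory-derived route into either count?** None is written.
- SAP 7.7.1 uses CTCAE laboratory grades for shift tables and for onset and duration of hematologic abnormalities. It does not link them to the DLT count or the stopping rule.
- The SAP 7.7.3 rule that keeps the most severe rating applies when the same AE is reported at several severities. It does not restore an abnormality that was never recorded as an AE.
- Hy's Law biochemistry is the exception: Section 8.4 makes it a DLT and Appendix 2 makes it an SAE on the laboratory values.

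**2. The plan's boundaries.** With prior Beta(0.4, 1.6) and x events in n subjects, the posterior is Beta(0.4 + x, 1.6 + n − x). The rule pauses at the smallest x with P(rate > 0.20) ≥ 0.80.
- n = 10: x = 3 gives 0.720, x = 4 gives 0.895
- n = 20: x = 5 gives 0.666, x = 6 gives 0.826
- n = 30: x = 8 gives 0.783, x = 9 gives 0.885

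The boundaries 4, 6 and 9 in Table 9 are confirmed.

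**3. The plan's operating characteristics.** I used an exact sequential binomial calculation with looks at 10, 20 and 30 and a maximum of 40. At true rates 0.10, 0.15, 0.20, 0.25 and 0.30, the pause probability is 2.05, 9.73, 25.79, 47.73 and 69.20%, and the average size is 39.5, 37.6, 33.9, 28.8 and 23.4. Table 10 states 2.1, 9.7, 25.8, 47.7 and 69.2%, with 39, 38, 34, 29 and 23. Tables 9 and 10 are therefore correct provided every Grade 4 or higher related event is recorded at that grade.

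**4. Effect of lost events.** Let p be the true rate and m the share of subjects with a Grade 4 or higher related event for whom every such event is a laboratory abnormality replaced by a lower-grade sequela. The recorded rate is p(1 − m). The documents give no value for m, so the range is an assumption. At p = 0.30 the recorded rates are 0.30 × 0.9 = 0.27, 0.30 × 0.8 = 0.24 and 0.30 × 0.7 = 0.21.

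| True rate | m = 0 | m = 10% | m = 20% | m = 30% |
|---|---|---|---|---|
| 0.25 | 47.7% | 36.4% | 25.8% | 16.7% |
| 0.30 | 69.2% | 56.7% | 43.2% | 29.9% |
| 0.40 | 94.1% | 87.4% | 76.4% | 61.1% |

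At p = 0.30 the average expansion size rises from 23.4 to 26.6, 29.9 and 32.9. At m = 0 nothing changes.

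**5. How far the DLT count is exposed.** A lost laboratory event still yields a DLT in most settings:
- a Grade 3 or higher sequela normally qualifies through the catch-all;
- febrile neutropenia is listed in its own right;
- permanent discontinuation of either drug, or a delay of more than 2 weeks in starting Cycle 2, counts;
- Hy's Law cases count.

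What remains is mainly sequelae of Grade 2 or lower. The stopping rule has no such backstop: any Grade 1 to 3 sequela that replaces a Grade 4 abnormality removes the event.

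**The case against.** **Section 8.4 is the more specific text.** It names the Grade 4 cytopenias as DLTs in themselves. The sentence in 8.2.6 opens with a qualifier and follows one that makes treated laboratory changes AEs. Table 6 calls for interruption of RMC-4630 for Grade 3-4 thrombocytopenia, so those events meet that AE test. Appendix 3 also prefers a diagnosis to individual signs and symptoms. All of this stands. A reader might infer that Grade 4 laboratory toxicities are certain to drop out of both counts; the documents show conflicting instructions and do not establish that outcome.

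**The information is not destroyed.** A reader might infer that the thrombocytopenia-with-bleeding criterion can never be identified. That is too strong: the bleeding is recorded as an AE, Appendix 2 requires laboratory results in the eCRF, and the Dose Committee reviews the safety data, with mTPI-2 only as its guide. This makes the conflict repairable, but no text tells anyone to use those values for either count.

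**Appendix 3.** The parenthesis could be read as excluding laboratory changes that need treatment, the reverse of 8.2.6. It can equally be read as two alternatives, which agrees with 8.2.6. It is an awkward sentence and not a demonstrated contradiction.

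**The percentages rest on an assumed m.** This is correct; they show sensitivity and are not estimates. Crossing a boundary also only pauses enrollment pending review, and the review may end in no change.

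**Conclusion.** The concern holds as an unresolved conflict between Section 8.2.6 and the AE-based counts in Sections 8.4 and 9.4.2 and SAP 7.7. The stopping rule is the more exposed of the two. Tables 9 and 10 are computed correctly, but their operating characteristics apply only if related Grade 4 laboratory events are recorded as Grade 4 AEs, and 8.2.6 as worded does not secure that. The DLT exposure is narrow. Grade 4 laboratory events without a sequela and Hy's Law cases are unaffected.

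The direction of any error is fixed: fewer recorded high-grade events, so a slower pause and severity tables that look better than they should. Its size is unknown and could be zero. The illustrated falls in pause probability assume that losses strike affected subjects independently at rate m and that sites follow 8.2.6 literally. Because a short change removes the dependence on site interpretation, the point should be corrected.

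**What to change.** 1. **Section 8.2.6.** Reconcile it with 8.4 and 9.4.2 by stating that a related laboratory abnormality is recorded as its own AE, with its own CTCAE grade and in addition to any clinical sequela, if it meets a Section 8.4 criterion, or if it is Grade 3 or higher and meets the AE definition.
2. **SAP 7.7.** State that a subject counts toward the stopping boundary on the highest recorded grade among related AEs, laboratory or clinical.
3. **Appendix 3.** Reword the parenthesis so that laboratory changes needing treatment or a change of study therapy are plainly AEs, as in 8.2.6.

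The trigger should not extend to every abnormality named in Table 6. That would draw in Grade 1-2 thrombocytopenia and Grade 1 liver tests, which neither count uses.

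The cost is about three sentences, a few extra AE lines in the eCRF, and slightly less favourable laboratory AE rates. No dose, DLT criterion or stopping boundary changes. If expansion enrollment has already finished, which the documents do not say, the benefit is limited to the final safety tables, and already recorded sequelae would need checking against the laboratory values in the eCRF.
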